Due to continuous evolution of influenza glycoproteins, the World Health Organization (WHO) meets to consider and make recommendations for updates in influenza vaccine composition twice a year. For the northern hemisphere, the WHO generally makes these recommendations in February. The U.S. Food and Drug Administration (FDA) Vaccines and Related Biological Products Advisory Committee (VRBPAC) subsequently meets in late February or early March to determine composition of the vaccines to be produced, distributed, and administered in the United States starting late summer of the same year. Since the 1940s, standard IIV manufacturing has involved the use of embryonated hen eggs. While effective, this technology is hampered by the requirement for pathogen-free eggs and specialized manufacturing facilities in which throughput can only be amplified by increasing the number of eggs. This process is also vulnerable to avian influenza viruses. Finally, the lengthy production process hinders potential for rapid scale-up in response to emerging needs such as a pandemic or supply shortage.

HHS has supported development of alternate influenza vaccine technology as a component of influenza preparedness. ¹³ In January 2013 the U.S. FDA approved Flublok®, the first recombinant influenza vaccine (RIV), RIV contains influenza virus antigens manufactured using an insect baculovirus expression system and recombinant technology. RIV does not contain ovalbumin. FDA licensed a quadrivalent formulation of RIV, Flublok® Quadrivalent (RIV4) in 2016. ¹⁴ RIV may offer some advantages to eggbased vaccines. Production time during a pandemic may be shorter, and permit earlier availability of vaccine (though this has not yet been demonstrated). In addition, it is not subject to egg-adaptation mutations that can occur in influenza vaccine virus strains as they are passaged through eggs. Some evidence suggests that such mutations may affect vaccine effectiveness. ¹⁵ However, specific effectiveness data for RIV are currently limited due to its relatively limited use to date.

In 2017, ACIP expanded its influenza vaccine recommendation for pregnant women to include RIV with no stated preference between RIV and IIV products.⁶ Data on uptake of RIV in pregnant women following the 2017 ACIP recommendations to include this vaccine in its maternal influenza recommendations are not available. Data from CDC's Vaccine Safety Datalink (VSD) suggest that use of RIV in the adult population has been

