7.3.16 Further analysis

Prior to the second season of enrollment, randomization was stratified by gestational age (<20 weeks versus 20-34 weeks) and by site. Stratification by gestational age was removed from Version 2.1 due to an error in the randomization schema noted after the first season. The overall randomization to RIV4 vs IIV4 was maintained but the gestational age stratification was unbalanced due to the error.

If the error in stratification by gestational age results in an imbalance in gestational age between the treatment groups, evaluation of secondary outcomes by treatment group will be done using gestational age as a covariate if specified analyses can adjust for this factor. To have reasonable results, each cell count needs to be 5 or greater.

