## 4 STUDY DESIGN

### 4.1 Study Description

This study is a prospective, randomized clinical trial of approximately 430 pregnant women enrolled at Duke University Medical Center (Lead Contractor), Cincinnati Children's Hospital Medical Center (Contributing Contractor), and Boston Medical Center (Contributing Contractor). Pregnant women  $\geq 18$  years of age at  $\leq 34$  weeks gestation, will be enrolled and randomized 1:1 to receive either quadrivalent recombinant influenza vaccine (RIV4) or quadrivalent inactivated influenza vaccine (IIV4). The designated vaccine brands for this study are Flublok® quadrivalent (Sanofi) and quadrivalent Flulaval® (GSK) (comparator

IIV4). However, the choice of IIV4 vaccine administered will be based on availability from manufacturers prior to the 2019-2020 and 2020-2021 influenza seasons.

After vaccination, participants and their infants will be followed to assess adverse pregnancy and birth outcomes, maternal vaccine reactogenicity, immunogenicity, serious adverse events, and short-term infant outcomes. Maternal and infant outcomes will be collected by medical record review from enrollment through 90 days postpartum.

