#### **4.2 Laboratory**

**Serologic studies** – We will evaluate pre- and post-vaccination serologic responses in both IIV4 and RIV4 groups. IgG levels will be measured for the specific viral strains included in the 2019-2020 and 2020-2021 quadrivalent influenza vaccines using hemagglutination inhibition assays at the Duke Regional Biocontainment Laboratory (RBL) Virology Unit. Venous blood (approximately 15 mL of blood) will be collected from each participant before and 29 (-7 to +14) days after vaccination. At Duke, maternal and infant cord blood (approximately 15mL of blood each) collection will be performed at delivery for serological analysis in both RIV4 and IIV4 vaccination groups. At the other sites, these samples (maternal and cord blood) will be collected during delivery only if feasible for similar serological analysis. An assessment of placental antibody transfer (maternal:cord antibody ratio) will be determined.

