#### **4.3 Sample Size and Power**

Allowing for a 5% drop out rate and given an initial N=430, there should be approximately 408 pregnant women participants for evaluation. We assume that 15% of pregnant women will have adverse birth outcomes after vaccination with RIV4 or IIV4, based on national and CISA site estimates of preterm birth rates. We have selected a clinically meaningful noninferiority margin of 10%. Statistical calculations show that with a one-sided alpha of 0.025 and 204 subjects in each group across all study sites, there is approximately 81% power to reject the null hypothesis that RIV4 is inferior to IIV4 in the proportion of adverse birth outcomes.

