#### **5.2 Analytic Issues**

There are three study sites participating in the study and analysis of the primary objective will be stratified by site (Duke, Boston, Cincinnati) to account for this unit of randomization. All objectives will be stratified by site when applicable. There is one primary objective being evaluated, using a noninferiority hypothesis at the one-sided alpha 0.025 level. Otherwise, the alpha level will be set at two-sided alpha 0.05 for the secondary objectives and all exploratory objectives.

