## 7 BASELINE DATA AND FLOW CHART

### 7.1 Presentation of Baseline Data

The following baseline information will be presented by treatment group, age, ethnicity, race and tobacco, marijuana or other substance use, gestational age at vaccination, study enrollment site, and influenza season of enrollment. Summary statistics (e.g., mean, standard deviation, median) will be presented for continuous variables. Categorical variables will be described with frequencies and percentages. Specific medical issues (i.e., hypertension, diabetes, and prior preterm birth) will also be presented.

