The proportion of infants with medically-attended events through 90 days of life and the proportion of infants with neonatal death will be compared between the RIV4 group and the IIV4 group using an exact Mantel-Haenszel statistic (calculated in Proc Logistic in SAS) in a stratified analysis by site to control for the randomization blocks at the two-sided alpha 0.05 level. The proportion and 95% exact binomial confidence interval of SAEs in infants through 90 days of life, as well as the total number of events, will be presented by site, vaccine group, severity, and relatedness. Listings of these SAEs will also be presented. Non-overlapping confidence boundaries will be an indication of a statistical difference between the groups.

5. EO5: To compare maternal immune responses to influenza antigens and calculate the post and pre-vaccination ratio after RIV4 versus IIV4 vaccination.

The proportion of pregnant women achieving seroconversion at day 29 and the proportion pregnant women with a seroprotective HAI titer ( $\geq 1:40$ ) pre- and post-immunization at day 29 will be compared using a Mantel-Haenszel statistic in a stratified analysis by site to control for the randomization blocks at the two-sided alpha 0.05 level. The geometric mean HAI titer (GMT) pre- and post-immunization at day 29 after RIV4 versus IIV4 vaccination for each influenza vaccine antigen will be compared (within vaccine arm pre versus post and within timeframe RIV4 versus IIV4) using a regression model with the log transformed titer value at the two-sided alpha 0.05 level. The proportion and 95% exact binomial confidence interval will also be presented in tabular format for each group. The Immunogenicity Population is the primary analysis population. The Maternal Immunogenicity Population is the primary analysis population.

6. EO6: To compare cord blood antibody levels for influenza antigens after RIV4 versus IIV4 vaccination.

The proportion of infants with cord blood seroprotective HAI titer will be compared using a Mantel-Haenszel statistic in a stratified analysis by site to control for the randomization blocks at the two-sided alpha 0.05 level. Infant cord blood geometric mean HAI titer (GMT) for each influenza vaccine antigen will be compared using a regression model with the log transformed titer value at the two-sided alpha 0.05 level.

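### The exploratory antibody comparisons pool two influenza seasons with no season term, and the plan does not say how a component whose strain changed is handled; the cost is lost precision, not bias.

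*SAP*

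**What the plan says.** SAP 8.3 calls the maternal antibody objective EO5 and the cord-blood objective EO6. The Protocol treats them as Exploratory Objectives 4 and 5, in 7.3.11 and 7.3.12. The methods are the same in both documents.

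- **Binary endpoints** (seroconversion, seroprotection): a Mantel-Haenszel test stratified by site.
- **GMTs:** the pre-vaccination and Day 29 GMT "for each influenza vaccine antigen will be compared (within vaccine arm pre versus post and within timeframe RIV4 versus IIV4) using a regression model" on log titre. Cord-blood GMTs are handled in the same way. No covariate is listed for either model.
- **General rule**, SAP 5.2: "All objectives will be stratified by site when applicable".
- **Assay**, SAP 4.2: antibody is measured against the "specific viral strains included in the 2019-2020 and 2020-2021 quadrivalent influenza vaccines". Protocol 6.1 likewise ties the test viruses to one season's vaccine or the other's.
- **Strain changes**, Protocol 1.1: the WHO convenes to "make recommendations for updates in influenza vaccine composition twice a year".
- **Use of season:** season of enrolment is a baseline descriptor in SAP 7.1, which lists "study enrollment site, and influenza season of enrollment". It enters no immunogenicity analysis. The one extra adjustment planned (SAP 10, Protocol 7.3.16) is for gestational age and covers secondary outcomes only.

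**The concern.** Season can determine which virus a titre is measured against, and it may also carry a different level of pre-existing immunity. If mean log titre differs between seasons and season is not in the model, the difference goes into the residual variance of every Day 29 and cord-blood GMT comparison. The site-only Mantel-Haenszel tests lose efficiency in the same way. Protocol 4.2 excludes 2019-2020 participants from the second season, so season is a clean between-woman factor and is already recorded.

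There is also a gap in definition. Protocol 6.1 speaks of four strain-specific antibodies, but two seasons could involve more than four strains. The plan does not say how these map to the antigens being analysed. If an antigen means a vaccine component, one GMT could mix titres against two viruses. If it means a strain, the split for changed components is unwritten, and unchanged components are still pooled across seasons without adjustment. Either way, the choice should be written down before titres are seen.

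**Working it through.** **The plan's own figure.** SAP 4.3 sizes the primary endpoint with "one-sided alpha of 0.025 and 204 subjects in each group across all study sites", a 15% event rate in both arms and a 10-point margin, and states about 81% power. The standard error is sqrt(2 × 0.15 × 0.85 / 204) = 0.03536, so power is Φ(0.10/0.03536 − 1.960) = Φ(0.868) = 80.7%. The figure reproduces, but it does not bear on this point. The documents give no SD, power or sample size for any antibody endpoint.

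**Assumptions (not in the documents).** Within-season SD of log2 titre is 1.5, 2.0 or 2.5. The between-season shift d in mean log2 titre is 0.5 to 3. The share f of women in one season is 0.5 unless stated. Allocation is 1:1 within each season.

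**GMT comparisons.** Leaving season out changes the variance from SD² to SD² + f(1−f)d². The inflation factor is therefore VIF = 1 + f(1−f)d²/SD². For a comparison with 80% power when season is modelled, power without it is Φ(2.802/√VIF − 1.960). This does not depend on the number of women. Cells show VIF; power.

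| d (log2) | Fold shift | SD 1.5 | SD 2.0 | SD 2.5 |
|---|---|---|---|---|
| 0.5 | 1.4 | 1.03; 78.9% | 1.02; 79.4% | 1.01; 79.6% |
| 1 | 2 | 1.11; 75.7% | 1.06; 77.6% | 1.04; 78.4% |
| 2 | 4 | 1.44; 64.5% | 1.25; 70.7% | 1.16; 73.9% |
| 3 | 8 | 2.00; 50.8% | 1.56; 61.1% | 1.36; 67.1% |

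The last row is an extreme, shown for completeness.

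In sample-size terms, the loss is n(1 − 1/VIF). With SD 2.0 and 204 per arm, a 2-fold shift costs 204 × (1 − 1/1.0625) = 12 women per arm. A 4-fold shift costs 204 × (1 − 1/1.25) = 41.

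**Unequal seasons.** With d = 2 and SD 2.0, f = 0.3 gives VIF = 1 + 0.21 × 4/4 = 1.21 and power 72.1%. With f = 0.15, VIF = 1 + 0.1275 × 4/4 = 1.13 and power is 75.1%. Equal seasons give 70.7%.

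**Seroprotection.** This was simulated with 40,000 replicates, 204 per arm split equally over two seasons, an odds ratio of 1.9, and no site strata in either version of the test.

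| Control rate by season | Power, season strata | Power, no season strata | Type I error, no season strata |
|---|---|---|---|
| 70% / 70% | 78.3% | 78.5% | 5.1% |
| 80% / 60% | 77.1% | 76.0% | 4.4% |
| 90% / 50% | 72.3% | 66.2% | 3.0% |
| 95% / 40% | 68.3% | 54.7% | 1.5% |

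Without season strata the test becomes conservative as the seasons diverge. It does not reject too often.

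**Within-woman measures.** If the shift is the same at baseline and at Day 29, log2(post) − log2(pre) removes it. The cord/maternal ratio behaves in the same way.

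**The case against.** The strongest reply is that the size is wholly assumed. No passage says that any strain changed between 2019-2020 and 2020-2021; Protocol 1.1 shows only that composition is reviewed. For a shift of 2-fold or less the loss is at most about four power points. It partly cancels in post/pre and cord/maternal ratios, and baseline titre, if modelled, could absorb some of the rest. The objectives are exploratory. All of this stands and limits the priority. It does not remove the omission, which is cheap to repair.

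A reader might infer four stronger points that the documents do not support.

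- **Bias.** Allocation is 1:1 in permuted blocks within site in both seasons, so an arm-by-season imbalance at randomisation arises only by chance. The analysed set depends on available samples, so exact balance is not guaranteed. A 5-point imbalance (about 0.05 × 204 = 10 women) would move a GMT ratio by 2^(0.05d): 1.035-fold for d = 1 and 1.072-fold for d = 2. That is chance error, not systematic bias.
- **Two randomisation schemes.** Protocol 7.3.16 says "Stratification by gestational age was removed from Version 2.1 due to an error in the randomization schema noted after the first season". But SAP 4.4 explains that REDCap drew only from the list for under 20 weeks, so season 1 was in practice close to site-stratified, as season 2 was by design.
- **Comparator brand.** SAP 4.1 says "the choice of IIV4 vaccine administered will be based on availability from manufacturers". The Protocol's section on treatment assignment plans one brand for both seasons where feasible. A brand change would affect the IIV4 arm only, which is an arm-by-season interaction that a season main effect would not address.
- **Different viruses are pooled.** This is one reading of an ambiguous phrase. A changed strain could equally be treated as a separate antigen. What can be said is that the plan does not specify which.

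**Conclusion.** The point holds as a matter of precision and specification. Two seasons with possibly different test strains are compared without season in the Mantel-Haenszel strata or among any named regression terms, and the handling of a changed strain is not stated. Under the assumed SDs of 1.5 to 2.5 log2 and equal seasons, the loss from 80% power is about 0 to 1 point for a 1.4-fold shift, 2 to 4 for a 2-fold shift and 6 to 16 for a 4-fold shift. It is smaller with unequal seasons and nil without a shift. No systematic bias or inflated type I error follows. The primary and secondary conclusions are unaffected.

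**What to change.** In SAP 8.3 EO5 and EO6, and in Protocol 7.3.11 and 7.3.12:

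1. List the covariates of the log-titre regressions for Day 29 and cord-blood GMTs, with site and influenza season as factors.
2. Stratify the Mantel-Haenszel tests of seroconversion and seroprotection by site × season.
3. State whether an antigen means a vaccine component or a strain. Where a component's strain differs between seasons, report GMTs for each season-specific strain before any season-adjusted RIV4:IIV4 ratio.

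The change needs only SAP and Protocol wording and a variable already collected. The downside is up to 3 × 2 = 6 strata. Some may be sparse for cord blood, because sites other than Duke collect delivery samples only where feasible, and a stratum with women in one arm only contributes nothing to the test.

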6 LABORATORY ANALYSES

6.1 Influenza Laboratory Analysis

Flublok® quadrivalent (Sanofi) and quadrivalent Flulaval® (GSK) will be the designated study products. An alternate licensed IIV4 may be used in place of Flulaval® if there are unforeseen issues.

As such, reference wild-type, reassortant, or vaccine virus strains representative of the specific viral antigens included in the 2019-2020 or 2020-2021 influenza vaccines will be used to evaluate the relative levels of all four influenza strain-specific antibodies in maternal serum (pre- and post-vaccination) and infant cord blood. To accomplish these activities all patient samples will be interrogated for influenza antibodies against the strains of interest using the influenza hemagglutination inhibition assay (HAI). This assay is considered the "gold-standard" measure by which to evaluate seroconversion/seroprotection in response to seasonal influenza vaccination. This assay will be performed in accordance with the Duke RBL Virology Unit's fully optimized and approved SOP (RVUSOP004 Influenza HI of Serum Samples). Briefly, test samples will be assayed by HAI as duplicate 2-fold dilution series starting at 1:10. Serum dilutions are then incubated with a concentration of virus verified to possess a known potential for red blood cell (RBC) agglutination. The presence of virus-specific antibodies is visualized via incubation of the virus-serum mixture with a RBC solution; the endpoint titer for a given dilution series is then expressed as the reciprocal of the final dilution in which complete HAI is observed. By convention, seronegative samples are defined as having an endpoint HAI titer < 1:40 and seropositive samples as having an endpoint titer of ≥ 1:40; and seroconversion as a HAI titer ≥ 1:40 at day 29 if the baseline titer is < 1:10 or a minimum four-fold rise in HAI titer if the baseline titer is ≥ 1:10 for each influenza vaccine antigen.

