#### **3.3 Exploratory**

- a)
  - 1. EOM1.1: Frequency and descriptions of serious adverse events in pregnant women vaccinated with RIV4 versus IIV4 during the 42 days after vaccination.
  - 2. EOM1.2: Frequency and descriptions of serious adverse events in pregnant women vaccinated with RIV4 versus IIV4 during the study
- b)
  - 1. EOM2.1. Proportions of infants born small-for-gestational age after RIV4 versus IIV4 vaccination.
  - 2. EOM2.2: Proportion of pregnant women with clinical chorioamnionitis after RIV4 versus IIV4 vaccination.
  - 3. EOM2.3: Proportion of women with preeclampsia or eclampsia after RIV4 versus IIV4 vaccination.

c)

1. EOM3.1: Proportion of infants with medically-attended events through 90 days of life after maternal RIV4 versus IIV4 vaccination.
2. EOM3.2: Frequency and description of SAEs in infants through 90 days of life after maternal RIV4 versus IIV4 vaccination.
3. EOM3.3 Proportion of infants with neonatal death after maternal RIV4 versus IIV4 vaccination.

d)

1. EOM4.1: Proportion of pregnant women achieving seroconversion at day 29 after RIV4 versus IIV4 vaccination [a Hemagglutination Inhibition Assay (HAI) titer  $\geq 1:40$  at day 29 if the baseline titer is  $< 1:10$  or a minimum four-fold rise in HAI titer if the baseline titer is  $\geq 1:10$ ) for each influenza vaccine antigen].
2. EOM4.2: Proportion of pregnant women with a seroprotective HAI titer ( $\geq 1:40$ ) post-vaccination at day 29 after RIV4 versus IIV4 vaccination for each influenza vaccine antigen.
3. EOM4.3: The maternal geometric mean HAI titer (GMT) pre and post-vaccination at day 29 after RIV4 versus IIV4 for each influenza vaccine antigen and the post/pre-vaccination ratio.

e)

1. EOM5.1: Proportion of infants with cord blood seroprotective HAI titer ( $\geq 1:40$ ) for each influenza vaccine antigen after maternal RIV4 versus IIV4 vaccination.
2. EOM5.2: Infant cord blood geometric mean HAI titer (GMT) for each influenza vaccine antigen after maternal RIV4 versus IIV4 vaccination.
3. EOM5.3: Ratio of cord blood to maternal influenza antibody titers at time of delivery for each influenza vaccine antigen after maternal RIV4 versus IIV4 vaccination.

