#### **6.3 Maternal Immunogenicity Population**

The Maternal Immunogenicity Population is a subset of the mITT Population that includes only pregnant women participants who received study vaccine, provide baseline and post-vaccination Visit 4 blood draws available for analysis within the protocol-defined time frame,

and with no major protocol violations affecting immunogenicity as determined by the study investigators.

The mITT Population is the primary analysis population for the safety and health outcomes analyses, with the PP Population as a confirmatory analysis population. The Immunogenicity Population is the primary analysis population for maternal immunogenicity outcomes (Exploratory Objectives 5); otherwise the mITT Population will be used for the Exploratory Objectives.

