## **10 FURTHER ANALYSIS**

If the error in stratification by gestational age results in an imbalance in gestational age between the treatment groups, evaluation of secondary outcomes by treatment group will be done using gestational age as a covariate if specified analyses can adjust for this factor. To have reasonable results, each cell count needs to be 5 or greater.

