## **APPENDIX 1**

### **Major Protocol Violations for Analysis**

1. Major Protocol Violations for Exclusion from Per Protocol Populations:
  - a. Age < 18 years of age at enrollment
  - b. Gestational age >34 weeks at vaccination
  - c. Did not provide written informed consent prior to vaccination
  - d. End of participation in study (e.g. loss to follow-up, early termination/withdrawal) prior to end of pregnancy
  - e. Receipt of the year's influenza vaccine (2019-20 or 2020-21) prior to study enrollment
  - f. Study participation in both 2019-20 and 2020-21 influenza season
  - g. Receipt of live vaccine while participating in this study or receipt of non-study vaccine within 7 days before or during the 8 days post-vaccination period.
  - h. Receipt of experimental drugs or medical device while participating in this study
  - i. Known multi-fetal gestation or fetal congenital anomaly at the time of enrollment, e.g. genetic abnormality or major congenital malformation based on antenatal ultrasound before randomization
2. Major Protocol Violations for Exclusion from Immunogenicity Populations:
  - a. No vaccine received
  - b. No pre- and/or post-vaccination blood draw
  - c. Receipt of any other vaccine between the pre- and post-vaccination blood draws
  - d. New immunosuppression disorders between the pre- and post-vaccination blood draws or receipt of immunosuppressive medication between the pre- and post-vaccination blood draws
  - e. Subject who was inadvertently enrolled and randomized to the study, though they were later learned to have had met the following criteria for study exclusion that would have affected immunogenicity
  - f. Influenza vaccine receipt during the current influenza season prior to study enrollment
  - g. Use of oral, antenatal, or parenteral corticosteroids ( $\geq$  20mg/day prednisone equivalent) or high-dose inhaled glucocorticoid for  $\geq$  14 consecutive days within the preceding 30 days
  - h. Has an active neoplastic disease (excluding non-melanoma skin cancer), a history of any hematologic malignancy, current bleeding disorder, or taking anticoagulants (a daily aspirin is acceptable)
  - i. Has a history of receiving immunoglobulin or other blood product (with exception of Rh immunoglobulin) within the 3 months prior to study vaccination

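### The Day 29 GMT comparison between arms names no baseline titre as a covariate, although every woman analysed has one; the comparison is valid but gives away precision

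*SAP*

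**What the plan says.** SAP 8.3 EO5 (the objective numbered EO4 in SAP 2.3 and in Protocol 7.3.11) compares GMTs before vaccination and at Day 29 "within vaccine arm pre versus post and within timeframe RIV4 versus IIV4) using a regression model with the log transformed titer value", at two-sided alpha 0.05. Protocol 7.3.11 uses the same words. Neither lists a covariate.

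Two general sections could supply one:
- SAP 5.2: "All objectives will be stratified by site when applicable". This adds site only.
- SAP 10: if gestational age turns out imbalanced, "evaluation of secondary outcomes by treatment group will be done using gestational age as a covariate". This is conditional and limited to secondary outcomes, whereas immunogenicity is exploratory.

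Baseline titre is nevertheless guaranteed. Under SAP 6.3 the Maternal Immunogenicity Population contains only women who "provide baseline and post-vaccination Visit 4 blood draws available for analysis", and SAP Appendix 1, item 2b, lists as grounds for exclusion "No pre- and/or post-vaccination blood draw".

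Baseline enters this objective in other ways: through the definition of seroconversion, and through EOM4.3 in SAP 3.3, which asks for the GMTs "for each influenza vaccine antigen and the post/pre-vaccination ratio".

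**The concern.** A woman's HAI titre before vaccination usually tells something about her titre four weeks later. If it does here, part of the spread in Day 29 titres is predictable from data already in hand. A between-arm comparison that leaves this out has a wider confidence interval than it needs.

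The planned quantities that do use baseline do not fill the gap. Seroconversion reduces the change to yes or no. The post/pre ratio subtracts baseline on the log scale instead of regressing on it, and the SAP specifies no between-arm test for it.

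The same unspecified sentence also covers the pre-vaccination contrast and the within-arm contrast. One analyst could therefore fit an unadjusted model and another an adjusted one, for each of the four antigens. At stake is the precision and reproducibility of the GMT ratio, not the validity of the trial.

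**Working it through.** The documents state no power or precision figure for this comparison. Their only power figure concerns the primary endpoint and does not bear on this point.

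**Inputs from the documents**
- Allocation 1:1 and "204 subjects in each group across all study sites" (SAP 4.3). This is an upper limit here, because the immunogenicity population is a subset of those vaccinated.
- Three sites (SAP 5.2).
- HAI read as "duplicate 2-fold dilution series starting at 1:10" (Protocol 6.1).

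**Assumptions, because the documents are silent**
- Correlation rho between baseline and Day 29 log titre: 0.3, 0.5 or 0.7.
- Underlying SD of 2 log2 units at both visits, a four-fold rise and an arm difference of 0.3 log2.
- Median baseline 1:10, 1:20 or 1:40, which puts 50%, 31% or 16% of baselines below 1:10. Titres below 1:10 are set to 1:5.

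**Step 1: validity.** In simulated trials with no true difference (3000 per value of rho, 204 per arm, rho 0 to 0.7), both analyses were unbiased. Type I error was 4.8% to 5.7% unadjusted and 4.6% to 5.3% adjusted.

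**Step 2: gain on a continuous scale.** The adjusted width relative to the unadjusted width is sqrt(1 - rho²):
- rho 0.3: sqrt(0.91) = 0.954
- rho 0.5: sqrt(0.75) = 0.866
- rho 0.7: sqrt(0.51) = 0.714

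As an equivalent unadjusted sample size per arm: 204/0.91 = 224, 204/0.75 = 272 and 204/0.51 = 400.

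**Step 3: gain on the HAI scale.** Rounding to two-fold steps and flooring at 1:10 weaken the correlation, to 0.26-0.29, 0.44-0.48 and 0.63-0.67. Widths relative to the unadjusted Day 29 comparison, with site in both the adjusted and unadjusted models (3000 runs per setting, 204 per arm):

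| Median baseline | Comparison | rho 0.3 | rho 0.5 | rho 0.7 |
|---|---|---|---|---|
| 1:10 | Adjusted for baseline | 0.966 | 0.898 | 0.779 |
| 1:10 | Post/pre log ratio | 1.07 | 0.94 | 0.78 |
| 1:20 | Adjusted for baseline | 0.961 | 0.885 | 0.754 |
| 1:20 | Post/pre log ratio | 1.11 | 0.96 | 0.78 |
| 1:40 | Adjusted for baseline | 0.959 | 0.878 | 0.740 |
| 1:40 | Post/pre log ratio | 1.15 | 0.98 | 0.78 |

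**Step 4: in terms of the GMT ratio.** The 95% interval is the estimate divided and multiplied by a factor. At median baseline 1:20:

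| Women per arm | Unadjusted | Adjusted, rho 0.3 | rho 0.5 | rho 0.7 |
|---|---|---|---|---|
| 204 | 1.30 | 1.29 | 1.27 | 1.22 |
| 150 | 1.36 | 1.35 | 1.32 | 1.26 |
| 100 | 1.46 | 1.44 | 1.40 | 1.33 |

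**Step 5: why the post/pre ratio is not a substitute.** Let k be the baseline SD divided by the Day 29 SD. Relative to the unadjusted comparison, the squared width is 1 + k² - 2·rho·k for the log ratio and 1 - rho² for the adjusted analysis. The difference is (k - rho)², which is never negative. With k = 1 the log ratio is wider than the adjusted analysis by a factor of 1.24, 1.15 or 1.08 for rho 0.3, 0.5 or 0.7. With equal SDs it is also wider than the unadjusted comparison whenever rho is below 0.5.

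**Step 6: cost if baseline carries no information.** With 408 women, an intercept, arm and two site terms leave 408 - 4 = 404 degrees of freedom. Adding baseline leaves 403. At rho = 0 the width grows by sqrt(1 + 1/403) = 1.001.

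**The case against.** The strongest reply is that nothing here is wrong. The planned comparison is valid, the objective is exploratory, and the phrase about a regression model is not a full specification, so baseline might be included. All of that stands. But the text does not say so, and the alternative readings matter: a joint model of both visits that forces a common baseline mean would recover the precision, while an arm-by-time model without that constraint gives the unadjusted Day 29 contrast when data are complete.

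The second reply is that the post/pre ratio already captures much of the gain. This is partly right. At rho 0.7 its simulated width is 0.78 of unadjusted, against 0.74 to 0.78 for the adjusted analysis, so little would be added if the ratio were compared between arms. At rho 0.5 the further reduction is about 4% to 10% (0.898/0.94 = 0.955; 0.878/0.98 = 0.896). At rho 0.3 the ratio is wider than the unadjusted comparison. The SAP states no between-arm test for it in any case.

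Three further cautions are fair:
- The size of the gain cannot be derived from the documents, and at rho 0.3 it would hardly change how a result is read.
- Lack of bias rests on randomization and also on exclusions from the immunogenicity population not differing by arm.
- The trial spans two seasons, whose vaccine strains may differ. Under one assumed pattern of opposing season shifts, with season left out of the model, the gain shrank, but adjustment still cost essentially nothing.

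**Conclusion.** The point holds as an optional improvement. The Day 29 comparison between arms is specified without baseline titre, although the population definition guarantees one for every woman analysed. The comparison remains valid, provided exclusions do not differ by arm, and the primary conclusion is untouched.

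The loss is in interval width: small if the correlation is about 0.3 (3% to 4%) and moderate if it is 0.5 to 0.7 (10% to 26%), measured against the unadjusted Day 29 comparison. These figures rest on the assumed correlation, SD and baseline distribution. The direction does not: in large samples the adjusted analysis is never less precise than either the unadjusted comparison or the log ratio, and its cost at zero correlation is negligible.

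**What to change.** In SAP 8.3 EO5, state that for each antigen the Day 29 GMT ratio (RIV4 to IIV4) and its 95% confidence interval come from an analysis of covariance of log Day 29 titre on arm, log baseline titre and site. Keep the post/pre ratio and seroconversion as planned. As a minor clarification, say that the pre versus post comparison within an arm is paired within woman.

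The cost is one or two sentences and one degree of freedom. Baseline titre and site are already collected, and no woman leaves the analysis. The wording in Protocol 7.3.11 can stay if the SAP gives the model.
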